 Based on previous research, in both groups, 25% of participants will accept QL when offered (Pilot 1, ongoing cessation R01); 42%, 31% and 27% will take 0, 1 and 2+ QL calls, respectively (ongoing cessation R01); and 12%, 13% and 31% will report quitting, respectively (ongoing cessation R01). In the QL+SFH group, 65% of those who decline QL will accept SFH (Pilot 2, SFH trials); of those accepting, 37% will create a SFH and 63% will not, with corresponding quit rates of 26% and 5% (SFH trials). We assume all who decline QL and SFH will quit at a very low rate (2%). Using these data to estimate cessation after a first offer of QL and SFH yields intent-to-treat quit rates of 5.9% (SFH) and 11% (QL+SFH). Even if no other cessation occurs, the study is powered to detect this difference. If we assume the same intervention use and quit rates apply for a second offer of QL and SFH (at 3-month follow-up), intent-to-treat quit rates would be 9.6% (SFH) and 17.5% (QL+SFH), also within the study's power. We are confident that the final quit rates for each group will fall between these values.

We used G\*Power to calculate the sample size required to detect study group quit rate differences of 6 vs 11% (minimum expected), 8 vs 14%, and 10 vs 17% (maximum expected) at three levels of power. As shown, with 1,116 participants (558 per group) completing 6-month follow-up, we can detect a 6 vs 11% difference with 85% power. Power will be greater for larger differences. Attrition is expected to be 40% at 6-month follow-up, thus a baseline sample of 1,980 assures enough participants at follow-up (n=1,188) even if attrition is slightly higher than projected.

**1.23** Will any data from this project be stored for use in future research studies?  
 Yes - contribution for future use is mandatory for participation in the study

**1.24** Does this project involve the collection or use of biological samples or genetic data?  
 No

**1.25** Are you requesting institutional certification to contribute human data or samples to a repository or database for broad sharing (public or restricted access)?  
 No

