Participants in Arm 1 of the study will be offered standard service: their state's tobacco quitline. Participants in Arm 2 will be offered the quitline first and if they decline, they will be offered Smoke-Free Homes.

**1.8** Check all materials that will be used in recruiting participants:

- Telephone script

Attachment Name	Category	Version	Date Attached
2-1-1 screening for SFH UpdateTRACKCHANGES 5.14.21.rtf	Recruitment Script: Phone	7	05/14/21

**1.9** Describe where the consent discussion will occur (check all that apply):

- By phone

**1.10** Participants and/or their legally authorized representative will have (check all that apply to the consent process):

- As much time as they desire to consider enrolling in the study, including:

- An opportunity to thoroughly review the consent materials with knowledgeable members of the research team, and with family and/or friends as appropriate
- Sufficient time to have all of their questions answered

**1.11** Provide a detailed description in sequential order of the study procedures following the consent process - DO NOT cut and paste from the Consent Document.

Describe study populations separately if they will be participating in different procedures

DESCRIBE:

- Control populations, if applicable
- Any randomization, if applicable
- What participants will be asked to do/what happens in the study (in sequential order)
- The time period over which procedures will occur
- Long-term follow-up and how it occurs

The recruitment and study procedures will occur for about 3 years and 3 months. Participants will be asked to participate in the study for a total of six months that may include completing the quitline coaching sessions which can take 1-4 months, Smoke-Free Homes which involves 3 mailings and 1 coaching call over the course of 6 weeks, and follow-up at 3 and 6 months; however, they can withdraw from the study at any time.

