Study Arm 1 will be the control group who will be offered their state tobacco quitline services following the baseline assessment. They will be given the option to enter this program. If they choose to do so, a Quit Coach from Optum will reach out to them and provide between 1 and 4 coaching calls to help them quit smoking. The specifics of each state quitline may vary slightly but the calls are scheduled to be flexible with the participant's availability. Quit Coaches use motivational interviewing and cognitive-behavioral techniques to help the participant set a quit date and be ready to quit. Programs also may have a printed Quit guide booklet, offer nicotine replacement therapy (NRT) like nicotine gum or patches, and provide texting and/or emailing services. Participants are also given a number that they can call whenever they need to.

Study Arm 2 will be the treatment group and they will also be offered their state tobacco quitline. What differs in this condition is that if participants are not interested in the quitline, they will be offered Smoke-free homes (SFH), which includes 3 mailings at 1 week, 4 weeks, and 6 weeks after enrollment and a coaching call at 2 weeks after enrollment. The SFH coach will discuss the steps of making their home smoke-free, goal-setting, and potential challenges and solutions.

All participants who complete the baseline assessment will be sent a \$25 grocery store gift card.

The first follow-up assessment will occur 3 months after the baseline assessment. The primary study outcomes are cessation-related. Participants will be asked if they smoked at all in the past 7 days and past 30 days to assess point prevalence abstinence. They will also be asked how many cigarettes per day they use if they still smoke and if they were able to create a smoke-free home if they are in the treatment group. Those who report any smoking in the past 7 days will be asked if they quit for at least 24 hours since the previous survey and to report on their nicotine dependence

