measured by the Heaviness of Smoking Index (cigarettes per day; time elapsed between waking and smoking). These items from the Fagerstrom Test of Nicotine Dependence are reliable over time with good predictive validity. All participants will report use of any pharmacologic cessation aids (i.e., NRT, bupropion, Chantix). Successful quitters (7 days) will report their confidence in staying quit and all others will report readiness to quit. Reactions to the quitline and smoke-free homes interventions and staff will be assessed with measures from our previous studies assessing usefulness (e.g., was it helpful?), satisfaction (would you recommend it to others?) user experience (were they easy to talk to?); coaches (similarity, liking, expertise, sincerity, trustworthiness); and intervention appropriateness (relevant to my life and situation, designed for someone like me). Participants who complete the assessment will be sent a \$25 gift card. Those who didn't quit smoking in the control group will be asked if they would like to try the quitline again. Those who didn't quit who were in the treatment group will be offered whichever program they weren't offered at baseline.

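### As worded, the 3-month re-offer rule in 1.11 gives Arm 2 no second Quitline offer while Arm 1 gets one, which biases Aim 2A's cumulative acceptance comparison against the study hypothesis

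*Combined protocol and SAP*

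**What the plan says.** - **Baseline (1.7 and 1.11).** Section 1.7 states: "Participants in Arm 2 will be offered the quitline first and if they decline, they will be offered Smoke-Free Homes". Section 1.11 agrees: "Study Arm 2 will be the treatment group and they will also be offered their state tobacco quitline". Every Arm 2 participant therefore gets a Quitline offer at baseline, and every Arm 2 decliner also gets a Smoke-Free Homes (SFH) offer.
- **Three months (1.11).** For Arm 1: "Those who didn't quit smoking in the control group will be asked if they would like to try the quitline again". For Arm 2: "Those who didn't quit who were in the treatment group will be offered whichever program they weren't offered at baseline".
- **Power section (1.21).** The higher pair of projected quit rates, 9.6% and 17.5%, is introduced with "If we assume the same intervention use and quit rates apply for a second offer of QL and SFH (at 3-month follow-up"). No subgroup is named as left out.
- **Analysis (1.20, Aim 2A).** Quitline acceptance and use is the primary implementation question. Acceptance is accumulated over the whole study period and compared by arm, and a higher value in Arm 2 counts as support for the hypothesis.
- **Attachments (1.13).** A 3-month follow-up instrument is listed, but its content is not part of the public document.

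**The concern.** The Arm 2 rule turns on what was not offered at baseline, and the Quitline was offered to all of Arm 2. Taken as written, the rule has these results:

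- Arm 2 Quitline accepters who have not quit are offered SFH.
- Arm 2 SFH takers are offered nothing.
- Arm 2 participants who declined both programs are offered nothing.
- Arm 1 non-quitters get a second Quitline offer.

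This contradicts 1.21. It also defeats the foot-in-the-door argument in 1.5 (claim 4), which needs the larger request to follow the smaller one: under the literal rule, nobody who takes SFH is asked about the Quitline again.

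Aim 2A is where it matters. If baseline decliners get two Quitline offers in one arm and one in the other, cumulative acceptance partly counts offers made rather than willingness to accept. The arm with fewer offers is the one the hypothesis favours.

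**Working it through.** **Inputs.** From 1.21: "25% of participants will accept QL when offered" (both groups); "65% of those who decline QL will accept SFH"; 42%, 31% and 27% of Quitline accepters take 0, 1 and 2+ calls, with quit rates of 12%, 13% and 31%; 37% of SFH takers create a smoke-free home (26% quit) and 63% do not (5% quit); those who decline everything quit at 2%. From 1.5: 73% contact at 3 months in the ongoing trial. Assumed: 990 per arm (1,980 / 2), two-sided 5% test, no true effect of SFH on Quitline acceptance, and all Arm 1 non-quitters re-asked.

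**Plan's own figures first.**
- Quit rate of Quitline accepters: 0.42×0.12 + 0.31×0.13 + 0.27×0.31 = 0.1744.
- Quit rate of SFH takers: 0.37×0.26 + 0.63×0.05 = 0.1277.
- Arm 1, one offer: 0.25×0.1744 + 0.75×0.02 = 5.9%. Arm 2, one offer: 0.25×0.1744 + 0.75×(0.65×0.1277 + 0.35×0.02) = 11.1%. Both match 1.21.
- Power for 6% vs 11% with 558 per group: 85.1%, as stated.

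**Arm 2 groups at baseline.** Accept the Quitline 25%; take SFH 0.75×0.65 = 48.75%; decline both 0.75×0.35 = 26.25%.

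**Cumulative Quitline acceptance.** Let f be 3-month contact and a the uptake of a second offer. Quitters are not re-offered.
- Arm 1: 0.25 + 0.75×0.98×f×a
- Arm 2 (a), literal rule: 0.25
- Arm 2 (b), only SFH takers re-offered the Quitline: 0.25 + 0.4875×0.8723×f×a
- Arm 2 (c), all non-quitting Quitline decliners re-offered: (b) + 0.2625×0.98×f×a

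At f = 0.73, with the gap as Arm 2 minus Arm 1 and, in brackets, the chance of a significant result against Arm 2:

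| Second-offer uptake | Arm 1 | (a) literal | (b) SFH takers only | (c) all decliners |
|---|---|---|---|---|
| 25% | 38.4% | 25.0%, −13.4 points (>99%) | 32.8%, −5.7 (75%) | 37.5%, −1.0 (6%) |
| 10% | 30.4% | 25.0%, −5.4 (76%) | 28.1%, −2.3 (20%) | 30.0%, −0.4 (4%) |
| 5% | 27.7% | 25.0%, −2.7 (27%) | 26.5%, −1.1 (8%) | 27.5%, −0.2 (3%) |

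For contact between 60% and 100%, the gap under (b) runs from −4.6 to −7.7 points at 25% uptake and from −1.9 to −3.1 at 10%. The small gap left under (c) arises because more Arm 2 decliners have quit by 3 months (0.65×0.1277 + 0.35×0.02 = 9.0%, against 2% in Arm 1) and so need no second offer.

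**Which rule fits the two-offer rates in 1.21?** The plan does not give its formula. The 2% is credited once here.
- Arm 1, all non-quitters re-offered, with the 2% going to those who decline twice: 0.0436 + (1 − 0.0586)×0.0436 + 0.5625×0.02 = 9.6%. Stated: 9.6%.
- Arm 2, literal: 0.25×(0.1744 + 0.8256×0.65×0.1277) + 0.4875×0.1277 + 0.2625×0.02 = 12.8%.
- Arm 2, SFH takers also re-offered the Quitline: add 0.4875×0.8723×0.25×0.1744, giving 14.7%.
- Arm 2, those who declined both also re-offered both: add 0.2625×0.98×(0.25×0.1744 + 0.75×0.65×0.1277), giving 17.4%. Stated: 17.5%.

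Other ways of crediting the 2% give 12.3–13.0%, 14.2–15.5% and 16.9–18.3% for the three Arm 2 rules, so the ordering does not change.

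**The case against.** The strongest reply is that this is one wrong word. Read 'accepted' for 'offered' and the rule makes sense: SFH takers get a Quitline offer and Quitline takers an SFH offer. People who declined both accepted neither program, so the corrected sentence can cover them too, and the 17.5% in 1.21 fits best if they are re-offered both. On that reading the Aim 2A gap is about 1 point or less. Staff also work from the 3-month script, which may already be right. And comparing cumulative acceptance under each arm's own offer sequence is a legitimate implementation question.

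Much of this stands. A reader might infer that even the 'accepted' reading shuts out those who decline both. The documents do not support that; the singular 'program' leaves them ambiguous, not excluded. A reader might also infer that the bias could run in favour of the hypothesis, if 'again' covers only Arm 1 participants who took the Quitline at baseline. The Arm 1 sentence states no such restriction, and the 9.6% is matched by re-offering all Arm 1 non-quitters.

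The reply does not rescue the text. Section 1.1 says there is no separate written protocol, so 1.11 is the visible procedure, and its rule is wrong as written. Section 1.21 is a conditional scenario, and its fit to one rule is inference. Comparing offer sequences is defensible only when the sequence is stated and intended, and the literal one contradicts the study's own rationale.

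**Conclusion.** The point holds as an error in the stated rule, with a bounded consequence. Followed literally, 1.11 would put Arm 2 about 13 points behind Arm 1 in cumulative Quitline acceptance at 25% second-offer uptake, or about 5 points at 10%, with no true difference in willingness. If the intended rule re-offers the Quitline to all non-quitting decliners, as 1.21 suggests, the gap is about 1 point or less. The intermediate rule gives about 6 and 2 points. These sizes rest on 73% contact, 990 per arm and the plan's uptake and quit rates. The 25% second-offer uptake is the plan's own assumption; the lower values are a range shown for sensitivity.

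A reader might infer that the trial's power depends on the second offer. It does not: the sample size rests on 6% vs 11%, the first-offer rates, and 1.21 says of that difference: "Even if no other cessation occurs, the study is powered to detect this difference". The abstinence analysis is likewise unaffected. Nor do the documents show that any participant was handled wrongly, since the 3-month script cannot be seen.

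**What to change.** In 1.11, replace both re-offer sentences with a rule to this effect:

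1. At 3 months, all non-quitters in both arms who declined the Quitline at baseline are offered it again on the same terms.
2. Arm 2 participants who decline it again and have not taken SFH are then offered SFH.
3. Arm 2 Quitline accepters who have not quit are offered SFH, plus any repeat Quitline offer that Arm 1 accepters receive.

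Check the 3-month script against this wording. In 1.20, Aim 2A, keep the cumulative comparison and add Quitline acceptance for the baseline and 3-month offers separately, with the number offered per arm. Treat the 3-month figures as descriptive, because that group is selected by quitting and by contact. If anyone has already been handled under the literal rule, interpret the cumulative result in light of the unequal offers.

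The cost is three sentences in 1.11, one in 1.20, and a log of each offer and its answer. If the script now omits those who declined both programs, it adds about 990×0.2625×0.98×0.73 = 186 Quitline offers in Arm 2. If it follows the literal rule, it also adds about 990×0.4875×0.8723×0.73 = 307 to SFH takers. No new participant measures are needed.

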The second follow-up assessment will occur at 6 months after baseline and will again be asked about smoking abstinence and their success in creating a smoke-free home. Those who report that they don't smoke will be offered to take an at-home urine cotinine test to verify their lowered nicotine levels. If participants are willing to participate, they will be mailed a urine test to measure their cotinine levels, which is a metabolite of nicotine. The urine test, which can be purchased at any local pharmacy over-the-counter, will be mailed to participants with instructions for sending the results. The study team will not receive any biological samples or testing materials in the mail. Instead, participants will be instructed to send a picture of their results to the study email account and/or phone account. The photo will include only the results: a photo of the dipstick next to the results card. No personal identifiable information will be included in the photo. The results will be linked to the participants study ID via their phone number from which the photo was sent. Consent will be obtained prior to sending the testing kit in the mail via phone script. Results will be recorded in participants study record. Incentives will be mailed to participants after result has been received by study team. Those who report a smoke-free home will be offered an in-home air monitoring kit. The study team will call participants to walk them through placing the monitor as well as how to send it back to use in one week. The study team will then send the filters from the kit to a lab for processing. A gift card will be sent once results are received.

**1.12** Will participants be randomized?

Yes

**1.13** Will any of the following be used to collect information from the participant or others?

- Screening questions or screening/eligibility questionnaires
- Surveys
- Questionnaires
- Stimuli
- Any other written assessments

Yes

Attachment Name	Category	Version	Date Attached
SFH 6mo followup CLEAN12.4.20.docx	Subject Data Collection Instruments	5	12/09/20
SFH baseline with text for callers 5-7-21 TRACK CHANGES.docx	Subject Data Collection Instruments	1	05/12/21
SFH baseline with text for callers 5-7-21 TRACK CHANGES-1.docx	Subject Data Collection Instruments	5	05/12/21
SFH 3mo followup Draft 6 071720_clean.docx	Subject Data Collection Instruments	5	09/09/20

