**Aim 1.** The primary effectiveness research question in this Hybrid Type 2 randomized trial is whether adding a Smoke Free Homes intervention to standard population-level cessation services will increase the proportion of low-income smokers who quit by 6-month follow-up. In this analysis, the independent and dependent variables are dichotomous; the strata variable is participants' state of residence, also a proxy for benefits offered by their state quitline. The primary outcome, self-report abstinence at 6-month follow-up, will be validated by urine cotinine test: Level 3-6 on the test strip will indicate continued smoking and Level 0-2 will confirm abstinence. Agreement between self-report and cotinine test result will be assessed using the Kappa statistic, with values > 0.75 viewed as excellent.

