Aim 1 will use intention-to-treat analyses, providing the most conservative estimate of intervention effects. With randomization and a large sample, we expect baseline characteristics to be similar by group. We will test for this using t-tests for continuous variables and chi-square tests for categorical variables. If significant differences are found, we will include those variables as covariates in all analyses. For Aim 1A (abstinence from smoking) the Cochran-Mantel-Haenszel test will be used to test the conditional association between study group and abstinence at 3- and 6-month follow-up, controlling for states. A Breslow-Day test will be used to examine whether there is a common odds ratio (OR) across states. Finding greater odds of abstinence across states for the group receiving both Quitline and Smoke Free Homes would support the hypothesized intervention effects. If the Breslow-Day test is significant, we will estimate state-specific ORs. To control for other potential covariates, we will regress abstinence at 3- and 6-month follow-up on study group and other covariates using logistic regression. In the regression model, 8 dummy variables for states will be created to account for differences in state Quitlines. Adjusted odds ratios (OR) and 95% confidence intervals (CI) will be reported to quantify the associations. Study group effects for Aim 1B (made a quit attempt or did not) will be examined in a series of analyses similar to those described for Aim 1A. Finding a greater odds of quit attempts in the Quitline and Smoke Free Homes group across states would support hypothesized effects. For Aim 1C, cigarettes smoked per day is a count dependent variable (DV) measured at baseline, 3- and 6-month follow-up and assumed to follow the Poisson distribution. If the assumption of Poisson distribution is met, we will regress the DV on study group, states and other potential covariates and allow the  $\beta$  for study group as a random effect using random-effect Poisson regression. Otherwise, we will fit random effect negative binomial regression to the data. Finding a larger decrease in cigarettes smoked per day in the combined group (vs. Quitline alone) would support the hypothesized effect. Analyses for Aim 1D will replicate those for Aims 1A-C, but be conducted in only the subset of participants from both groups who declined quitline services when offered at baseline. Regression analyses for Aim 1D will also test baseline variables described previously (see "Baseline survey"), because quitline acceptance rates may differ by group. These comparisons provide the best estimate of the added benefit of offering Smoke Free Homes to smokers who are not yet ready to quit.

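### Only self-reported non-smokers are offered the cotinine test, so the planned kappa is 0 or undefined and cannot show what share of claimed quits is confirmed

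*Combined protocol and SAP*

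**What the plan says.** **Who is tested (1.11, 6-month follow-up).** "Those who report that they don't smoke will be offered to take an at-home urine cotinine test to verify their lowered nicotine levels". Testing is voluntary. The kit is mailed, and the participant sends back a photo of the strip: "Consent will be obtained prior to sending the testing kit in the mail via phone script", and "Results will be recorded in participants study record". No section offers the test to participants who report smoking.

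**How a result is read (1.20, Aim 1).** "Level 3-6 on the test strip will indicate continued smoking and Level 0-2 will confirm abstinence".

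**How the validation is summarised (1.20, Aim 1).** "Agreement between self-report and cotinine test result will be assessed using the Kappa statistic, with values > 0.75 viewed as excellent". No other validation statistic is named, and no section plans to report the proportion of claimed quits that are confirmed.

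**The between-arm analysis (1.20, Aim 1A).** "the Cochran-Mantel-Haenszel test will be used to test the conditional association between study group and abstinence at 3- and 6-month follow-up", followed by logistic regression. The text does not say whether a Level 3-6 result changes a participant's abstinence status in these analyses.

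**Expected numbers (1.21).** The planning quit rates run from 6% vs 11% to 10% vs 17%, and "a baseline sample of 1,980 assures enough participants at follow-up (n=1,188) even if attrition is slightly higher than projected".

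**The concern.** Kappa compares observed agreement with the agreement expected by chance from the two sets of marginal totals. It needs both ratings to vary. If only people who say they do not smoke are tested, one rating has a single value and the self-reported-smoker row of the 2x2 table is empty.

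At stake is the evidence that supports a self-reported primary outcome. As written, a trial with 90% of tested claims confirmed and one with 50% confirmed would both report kappa = 0. Against a benchmark of 0.75, both would read as no agreement beyond chance. The quantity a reader needs, the share of claimed quits that the test supports, is not planned.

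**Working it through.** **1. The plan's own figure.** Section 1.21 gives 558 per group for 6% vs 11% at 85% power. Assuming two-sided alpha 0.05 and no continuity correction (neither is stated), with a mean rate of 0.085:

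n = [1.960 × √(2 × 0.085 × 0.915) + 1.036 × √(0.06 × 0.94 + 0.11 × 0.89)]² / 0.05² = 557.1, rounded up to 558.

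This reproduces the figure. Completers: 1,980 × 0.60 = 1,188, as stated. These numbers only set the scale; the result in step 3 does not depend on them.

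**2. How many would be offered the test.** Assume equal arms and equal retention (594 per arm), with the planning rates applied to completers:

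- minimum: 594 × 0.06 + 594 × 0.11 = 35.6 + 65.3, about 101
- maximum: 594 × 0.10 + 594 × 0.17 = 59.4 + 101.0, about 160

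**3. Kappa as planned.** Of n tested, x are at Level 0-2, and p = x/n. All n are self-reported abstainers.

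- Observed agreement: po = p
- Chance agreement: pe = 1 × p + 0 × (1 − p) = p
- Kappa = (po − pe)/(1 − pe) = 0/(1 − p), which is 0 for p < 1 and 0/0 for p = 1

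| Confirmed of 101 | po | pe | Kappa | Confirmed proportion (exact 95% CI) |
|---|---|---|---|---|
| 50 | 0.495 | 0.495 | 0.00 | 50% (39.4 to 59.6%) |
| 71 | 0.703 | 0.703 | 0.00 | 70% (60.4 to 79.0%) |
| 91 | 0.901 | 0.901 | 0.00 | 90% (82.5 to 95.1%) |
| 101 | 1 | 1 | undefined | 100% |

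The same tables that give an uninformative kappa give a usable proportion.

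**4. Precision of the replacement.** Assume 80% confirmed, with either all or half returning a result. The documents give neither figure. The arm half-width is 1.96 × √[0.8 × 0.2 × (1/n1 + 1/n2)]. Halved counts are rounded.

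| Scenario | Overall, exact 95% CI | Arm sizes | Half-width of arm difference |
|---|---|---|---|
| Minimum rates, all return | 81/101: 71.1 to 87.5% | 36, 65 | 16.3 points |
| Maximum rates, all return | 128/160: 73.0 to 85.9% | 59, 101 | 12.8 points |
| Minimum rates, half return | 40/50: 66.3 to 90.0% | 18, 33 | 23.0 points |
| Maximum rates, half return | 64/80: 69.6 to 88.1% | 30, 51 | 18.0 points |

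**5. Why the return rate must be reported too.** If 50 of 101 return a result and 40 are confirmed, the proportion is 40/50 = 80% among those tested but 40/101 = 40% of all claimed quits.

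**The case against.** **The trigger may be looser than the outcome.** Section 1.11 ties the offer to not smoking, without naming the 7-day or 30-day item. The 6-month instrument is listed in 1.13 but its text is not shown. If, for example, 7-day abstainers are tested and 30-day abstinence enters kappa, both rows could be filled and kappa would not collapse. This stands as a caveat. The documents do not say it, and such a kappa would still exclude people who admit smoking.

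**Kappa decides nothing.** No action follows from a value above or below 0.75, and the confirmed proportion can be computed from results already recorded. This is true and limits the severity. But the named statistic cannot do the job the plan gives it, and its replacement is better chosen before the data are seen.

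**Kappa could be rescued.** Testing a sample of self-reported smokers would make it estimable, but that adds testing, and the confirmed proportion would still be needed.

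**Stronger readings that a reader might infer:**

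- *The 0.75 benchmark is too lenient.* If the 1,087 untested smokers (1,188 − 101) were counted as cotinine-positive, kappa would be 0.752 with only 63 of 101 claims confirmed. The plan states no such coding, so this is illustrative only.
- *The treatment comparison is invalid.* The documents do not support this. The Cochran-Mantel-Haenszel and logistic analyses do not use kappa.
- *The confirmed proportion is conservative.* This is not supported either. Nicotine replacement, or smoking after the interview, lowers it. Voluntary return and a self-sent photo may raise it. The net direction is unknown.

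**Conclusion.** The point holds and should be fixed. On the text as written, kappa is 0 for every confirmed share below 100% and undefined at 100%. The benchmark cannot be met, and kappa cannot show what share of claimed quits is confirmed. This follows algebraically from who is offered the test and needs no assumption about quit rates, uptake or retention. It rests on the kappa variable being the same report of not smoking that triggers the offer, which the unseen 6-month instrument could qualify.

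The base of 101 to 160 tested assumes that the planning quit rates apply to 1,188 completers. Section 1.21 also describes its first-offer estimates as intent-to-treat. Applied to all 1,980 enrolled (990 per arm), the same rates give 990 × 0.17 = 168 to 990 × 0.27 = 267 claimed quits. That changes the precision, not the finding.

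The sample size is untouched. The between-arm analyses are unaffected provided they use self-reported abstinence and Level 3-6 results do not reclassify participants, which 1.20 leaves open.

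**What to change.** In 1.20, replace kappa and its benchmark with:

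1. the proportion of tested self-reported abstainers at Level 0-2, with an exact 95% CI, overall and descriptively by arm;
2. the share of self-reported abstainers in each arm who returned a result;
3. confirmed quits as a share of all self-reported abstainers, counting decliners and non-returners as not confirmed, labelled as a sensitivity figure.

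Two clarifications would help: in 1.20, whether a Level 3-6 result changes abstinence status in the Aim 1 analyses; and in 1.11, which abstinence window triggers the offer, unless the 6-month instrument already says so.

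**Cost.** This is wording only. It needs no extra testing, participants or data, because results are already recorded. The limits should be stated alongside: the proportion among those tested may be biased in either direction, and the arm comparison (half-width about 13 to 23 points under the assumptions above) is too imprecise to show that the arms have equal confirmation rates.
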